2.3 Rationale for dose and regimen selection

[REDACTED]

[figure not shown]
3 Objectives and endpoints

[figure not shown]
Objectives and related endpoints are described in [Table 3-1](#) below.

[figure not shown]
[REDACTED]

Table 3-1 Objectives and related endpoints

Objective	Endpoint	Analysis
Primary		
To demonstrate the antitumor activity of LDK378, as measured by overall response rate (ORR) to LDK378 by investigator assessment	ORR per RECIST 1.1 calculated as the proportion of patients with a best overall response defined as complete response or partial response (CR+PR) as assessed by investigator	Refer to Section 10.4.
Key secondary		
To evaluate response related endpoints as assessed by investigator and Blinded Independent Review Committee (BIRC):	The following endpoints will be evaluated by investigator assessment and BIRC per RECIST 1.1:	Refer to Section 10.5.1.
1. Duration of response (DOR)	1. DOR, calculated as the time from the date of the first documented CR or PR to the first documented progression or death due to any cause	
2. Disease control rate (DCR)	2. DCR, calculated as the proportion of patients with best overall response of CR, PR, or SD	
3. Time to Response (TTR)	3. TTR, calculated as the time from first dose of LDK378 to first documented response (CR+PR)	
4. Overall intracranial response rate (OIRR)	4. OIRR calculated as the ORR (CR+PR) of lesions in the brain for patients who have measureable disease in the brain at baseline	
And to assess:	And:	
5. ORR by BIRC assessment	5. ORR (CR+PR) per RECIST 1.1 as assessed by BIRC	
Other secondary		
1. To evaluate the safety profile of LDK378	1. Adverse events and laboratory abnormalities	Refer to Section 10.5.2.
2. To evaluate progression-free survival (PFS)	2. PFS, defined as time from first dose of LDK378 to progression or death due to any cause, as assessed by BIRC and investigator assessment	
3. To evaluate overall survival (OS)	3. OS, defined as time from first dose of LDK378 to death due to any cause	

Objective	Endpoint	Analysis
		

4 Study design

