7.2.2.5 Laboratory evaluations

Central laboratories will be used for the analysis of scheduled hematology, biochemistry and other blood specimens collected as part as safety monitoring. All unscheduled blood testing will be performed locally. Dipstick urinalysis will be performed locally, except in the case of any out of range parameter on scheduled local urine analysis, when a urine sample will be sent to central laboratory for further analysis. Details on the collection, shipment of blood, urine and tumor samples and reporting of results by the central laboratory are provided to investigators in a separate [\[Laboratory Manual\]](#). The time windows granted for laboratory evaluations are identical to the corresponding visit time windows for each visit (refer to [Section 7.1](#)).

Laboratory values obtained at the screening visit will be used to assess eligibility to meet inclusion criteria 7. In addition, eligible patients must have baseline laboratory assessments performed on Cycle 1 Day 1 / Run-in Day 1 or within 24 hours prior to dosing. The results of centrally-analyzed laboratory assessments performed at Cycle 1 Day 1 do not need to be received by the site prior to initiation of dosing.

[figure not shown]

Table 7-3 Clinical laboratory parameters collection plan

Test Category	Test Name
Hematology	Hemoglobin, platelets, white blood cells (WBC), red blood cells (RBC), differential (basophils, eosinophils, lymphocytes, monocytes, neutrophils [% or absolute])
Blood Chemistry	Albumin, ALT, AST, calcium (at screening calcium corrected for albumin), creatinine, creatinine clearance, total bilirubin, direct bilirubin (only if total bilirubin is \geq grade 2), blood urea nitrogen (BUN) or urea, magnesium, potassium, sodium, fasting glucose, phosphate (inorganic phosphorus), alkaline phosphatase, amylase, GGT, lipase
Urinalysis	Macroscopic panel (dipstick) (bilirubin, blood, glucose, ketones, WBC, pH, protein, specific gravity) Microscopic panel (RBC, WBC, casts)
Hormones (males only)	Testosterone, LH, FSH, sex hormone binding globulin (SHBG)
Coagulation	INR and pro-thrombin time (PT) or Quick Test

Details on the collections, shipment of samples and reporting of results by the central laboratory are provided to investigators in the [Laboratory Manual].

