10.5.3.3 Laboratory abnormalities

For laboratory tests covered by the CTCAE version 4.03, the study's biostatistical and reporting team will grade laboratory data accordingly. For laboratory tests covered by CTCAE, a Grade 0 will be assigned for all non-missing values not graded as 1 or higher. Grade 5 will not be used.

For some cases (e.g. white blood cell differentials), the lower limits of normal ranges used in CTCAE definitions will have to be replaced by a clinical meaningful limit expressed in absolute counts.

For laboratory tests where grades are not defined by CTCAE, results will be graded by the low/normal/high classifications based on laboratory normal ranges.

A listing of laboratory values will be provided by laboratory test, patient, and study day. A separate listing will display notable laboratory abnormalities (i.e., newly occurring CTCAE grade 3 or 4 laboratory abnormalities).

The following summaries will be generated separately for hematology and biochemistry laboratory tests:

- shift tables using CTCAE grades to compare baseline to the worst on-treatment value
- for laboratory tests where CTCAE grades are not defined, shift tables using the low/normal/high/(low and high) classification to compare baseline to the worst on-treatment value.

Listing of all laboratory data with values flagged to show the corresponding CTCAE grades and the classifications relative to the laboratory normal ranges will be generated.

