### 2.1 Data analysis

Data will be analyzed by Novartis Oncology Biostatistics and programming personnel according to the data analysis section 10 of the LDK378A2203 protocol. Important information is given in the following sections and details are provided, as applicable, in Section 4 from which Appendix 16.1.9 of the CSR will be extracted.

SAS® version 9.4 (or later version if available at time of database lock) will be used in all analyses.

Data from all patients who signed informed consent in centers that participate in this study will be used in the analysis; due to expected small size of enrollment at individual centers, no center effect will be assessed. Each analysis will use all data in the database up to the analysis cutoff date, determined prior to database lock.

As described in Section 1.1 this study has a Simon two-stage design. If the study stops at the end of Stage 1 (see Section 2.11), the data available will be summarized in an abbreviated CSR. Otherwise, the analysis cut-off date for the primary analysis of study data will be established once all patients have either completed at least six treatment cycles, i.e., 168 days (1 cycle = 28 days), or discontinued study drug earlier. The data will be summarized in the primary CSR. Following the primary analysis time point, the study will remain open. Patients still being followed on the study will continue as per the schedule of assessments.

The analysis cutoff date for the final analysis of study data will be 22-Jan-2018 corresponding to last patient last visit date.

[Section 4.1](#) provides further details regarding data to be included in the analyses.

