## **Laboratory data**

For laboratory data assessments, data from all sources (central and local laboratories) will be combined. The summaries will include all laboratory assessments collected no later than 30 days after study drug discontinuation. All laboratory assessments will be listed and those collected later than 30 days after study drug discontinuation will be flagged in the listings.

Laboratory data will be classified (by Novartis Oncology CORR) into CTC grades according to the NCI CTCAE v4.03. For all reports, CTC grade is always obtained on the converted

measurement in SI unit. A severity grade of 0 will be assigned when the value is within normal limits. Grade 5 will not be used.

The following summaries will be produced for the hematology and biochemistry laboratory data (by laboratory parameter):

- Shift tables using CTC grades to compare baseline to the worst post-baseline value for laboratory parameters with CTC grades
- Shift tables using low, normal, high (as well as low and high combined) classifications to compare baseline to the worst post-baseline value for laboratory parameters where CTC grades are not defined.

The following lab parameters will be summarized:

- Hematology: absolute lymphocytes (decreased), absolute neutrophils (decreased), hemoglobin (anemia) (decreased), WBC (decreased); platelet counts (decreased)
- Biochemistry: alkaline phosphatase (APL) (increased), SGPT (ALT) (increased), SGOT (AST) (increased), total bilirubin (increased), amylase (increased), potassium (hyper and hypo), sodium (hyper and hypo), creatinine (increased), glucose (hyper and hypo), phosphate (hypo)

The following laboratory parameters will be presented in listings and will not be summarized: absolute basophils, absolute eosinophils, absolute monocytes, RBC, albumin, calcium, magnesium, creatinine clearance, direct bilirubin, blood urea nitrogen (BUN) or urea, GGT, urinalysis macroscopic panel (dipstick) (bilirubin, blood, glucose, ketones, WBC, pH, protein, specific gravity), Urinalysis Microscopic panel (RBC, WBC casts), Hormones (males only) Testosterone, LH, FSH, sex hormone binding globulin (SHBG), coagulation INR, prothrombin time (PT) or Quick Test.

The following listings will be produced for the laboratory data for all laboratory parameters where CTC grades are defined:

- Listing of patients with laboratory abnormalities of CTC grade 3 or 4

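### SAP 2.8.2 restricts the protocol's laboratory shift tables to 15 named tests without declaring it, so magnesium, calcium and lipase have no laboratory-based summary table

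*SAP*

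**What the plan says.** Protocol Section 3 (Table 3-1) gives the safety endpoint as "Adverse events and laboratory abnormalities". Protocol 10.5.3.3 sets out how the laboratory part is to be summarized: "The following summaries will be generated separately for hematology and biochemistry laboratory tests". Two shift tables follow, one by CTCAE grade and one by low/normal/high for tests that have no grade. No list of tests is attached.

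Protocol Table 7-3 defines the panels. The blood chemistry row includes magnesium, "calcium (at screening calcium corrected for albumin" and, at its end, "alkaline phosphatase, amylase, GGT, lipase".

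SAP 2.1 says that data will be analyzed "according to the data analysis section 10 of the LDK378A2203 protocol". SAP 2.8.2 repeats the two shift tables and then names the tests to be summarized: five in hematology and ten in biochemistry, the latter including "total bilirubin (increased), amylase (increased), potassium (hyper and hypo), sodium (hyper and hypo". It continues: "The following laboratory parameters will be presented in listings and will not be summarized: absolute basophils, absolute eosinophils, absolute monocytes, RBC, albumin, calcium, magnesium", with further tests after that. Lipase is in neither list. The same section also says "All laboratory assessments will be listed".

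SAP Table 3-1 has one laboratory row. It deletes frequency tables of newly occurring grade 3 or 4 values, on the ground that the shift table carries similar information.

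**The concern.** The protocol's shift tables cover both panels, and the SAP narrows them to a closed list. SAP Section 3 exists to record such changes, and it records one that it describes as not a real change (the Safety Set wording). This narrowing is not there. The reason in the one laboratory row also fails for any test that has no shift table.

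Most of the omitted tests are no loss, but three are hard to square with the SAP's own choices:

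- **Magnesium and calcium.** Inclusion criterion 7 requires four analytes to be normal or corrected at entry: potassium, magnesium, phosphorus and calcium. The SAP tabulates only potassium and phosphate.
- **Lipase.** Protocol Table 6-3 applies one dose rule to amylase and lipase together. The SAP tabulates only amylase.

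What is at stake is the rate of laboratory-defined abnormality. Under protocol 8.1.1 an abnormal value is an adverse event only if it causes symptoms, is clinically significant, or leads to therapy or a change in study drug. Values of these three tests that meet none of these conditions appear in listings but are counted in no table.

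**Working it through.** There is no stated figure to reproduce. The check is a count of tests, document against document.

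**Inputs**

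- Protocol Table 7-3, hematology: hemoglobin, platelets, WBC, RBC, basophils, eosinophils, lymphocytes, monocytes, neutrophils = 9.
- Protocol Table 7-3, chemistry: albumin, ALT, AST, calcium, creatinine, creatinine clearance, total bilirubin, direct bilirubin, BUN/urea, magnesium, potassium, sodium, glucose, phosphate, ALP, amylase, GGT, lipase = 18.
- SAP 2.8.2, summarized: lymphocytes, neutrophils, hemoglobin, WBC, platelets = 5; ALP, ALT, AST, total bilirubin, amylase, potassium, sodium, creatinine, glucose, phosphate = 10.
- SAP 2.8.2, listing-only within these two panels: basophils, eosinophils, monocytes, RBC, albumin, calcium, magnesium, creatinine clearance, direct bilirubin, BUN/urea, GGT = 11.

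**Counts**

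| Quantity | Arithmetic | Result |
|---|---|---|
| Tests in the two panels | 9 + 18 | 27 |
| Summarized | 5 + 10 | 15 |
| Not summarized | 27 − 15 | 12 |
| In neither SAP list | 12 − 11 | 1 (lipase) |
| Omissions at issue, of chemistry tests | 3 / 18 | 16.7% |
| Entry electrolytes without a shift table | 4 − 2 | 2 of 4 |
| Pancreatic enzymes without a laboratory table | 2 − 1 | 1 of 2 |
| Left to declare as listing-only | 12 − 3 | 9 |

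**Can the three be tabulated?** Magnesium and calcium are in the chemistry panel taken at screening, at Cycle 1 Day 1 and through treatment (protocol Table 7-1), so a baseline-to-worst shift table is feasible. Calcium needs one decision first: Table 7-3 mentions albumin correction only at screening, and the SAP does not say which form would be graded on treatment.

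Lipase is different. The Amendment 3 change list shows that lipase was added to Table 7-3 by that amendment, whose rationale says that recruitment was complete and 124 patients had been treated. A scheduled baseline lipase value is therefore not expected for any patient. Unscheduled local values may exist, but the documents mention none. A worst post-baseline grade table is feasible; a shift table largely is not.

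**The case against.** The strongest reply is that the choice of tests is a matter of judgment and that little is lost.

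- **The protocol does not say every test.** True. The fix proposed here also accepts nine tests as listing-only, so 10.5.3.3 is not being read as an absolute rule. But the protocol gives no basis for a subset, and the SAP gives no reason for its own.
- **The choice may follow risk.** Hypokalemia is in protocol Table 1-1 (10.2% all grades, 4.3% grade 3/4), and hypophosphatemia has a dose entry and a management section. Magnesium and calcium have neither a Table 1-1 row nor a dose rule. This is a fair account of the electrolyte choice, though the SAP does not state it. It does not explain lipase, which has a dose rule.
- **The magnesium and calcium decision is open.** The SAP states it plainly, so for the 11 listing-only tests the missing SAP Table 3-1 row is a matter of record keeping. This stands. Only lipase is left unassigned. The general bullet on parameters with CTC grades could be read to include it, but the named list that follows does not.

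Three stronger readings are tempting, and the documents do not support them:

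- A reader might infer that these abnormalities reach no table at all. They can. Grade 3 or higher lipase requires a dose hold (protocol Table 6-3), which makes it an adverse event by definition (protocol 8.1.2.1), and the SAP tabulates lipase elevations under the pancreatitis AESI.
- A reader might infer that hypomagnesemia behind a QTc prolongation would go uncounted. The grade 3 QTc rule requires abnormal electrolytes to be corrected before study drug is resumed. A value that needs therapy is an adverse event and enters the AE tables.
- A reader might infer that a feasible lipase shift table was dropped. Lipase collection began too late to provide a scheduled baseline.

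**Conclusion.** The point holds in a limited form. SAP 2.8.2 narrows a protocol-planned summary of a named safety endpoint from two full panels to 15 of 27 tests, and SAP Table 3-1 does not say so. For magnesium, calcium and lipase, 3 of 18 chemistry tests, the result is no laboratory-based summary table.

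What goes uncounted is narrow: magnesium, calcium and lower-grade lipase abnormalities that cause no symptoms, are not judged clinically significant, and lead to no therapy or drug change. For lipase this means grades 1 and 2, where Table 6-3 maintains the dose. All values remain in listings, with CTC grade flags and a separate listing of grade 3 or 4 abnormalities for graded parameters. No efficacy result is touched.

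The documents give no laboratory-based rate for these three tests, so no patient count can be stated. The one related figure, grade 3-4 lipase increase in 5.1% of 255 phase I patients, is an adverse-event rate, which is the part that the AE tables already capture.

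The conclusion assumes that the SAP's named list governs the shift tables, which is its natural reading. This is an inexpensive improvement, not a flaw that threatens the trial.

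**What to change.** 1. In SAP 2.8.2, add magnesium and calcium (hyper and hypo) to the CTC-grade shift tables, using low/normal/high for any direction without a grade. State whether on-treatment calcium is albumin-corrected.
2. Add a table of worst post-baseline CTC lipase grade among patients with at least one post-baseline lipase value. Show that denominator, and note that lipase entered the collection plan with Amendment 3, after recruitment closed.
3. Add one row to SAP Table 3-1 declaring the other nine tests as listing-only, with the reason: albumin, GGT, creatinine clearance, direct bilirubin, BUN/urea, RBC, basophils, eosinophils and monocytes.

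The cost is SAP wording, one row in SAP Table 3-1, and three more parameters in laboratory table programs that are needed anyway. No data collection is added. The downside is a few extra table rows and a restricted lipase denominator. It will consist mainly of patients still being tested after Amendment 3, so the lipase rate should not be read as a rate for all treated patients.

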## ECGs

ECG data will be analysed based on central laboratory reported results. The summaries will include all ECG assessments performed no later than 30 days after the last date of study drug. All ECG assessments will be listed, and those collected later than 30 days after study drug discontinuation will be flagged in the listing.

The following analyses will be performed for each applicable ECG parameters (RR, PR, QRS, QT, ventricular rate, QTcB, QTcF, and QTcP) as noted.

- For each of the QTcF, QTcB, QTcP, and QT intervals, descriptive statistics at baseline, at each post-baseline time point and changes from baseline at each post-baseline time point
- For each of the QTcF, QTcB, QTcP, and QT intervals, shift tables based on notable parameter categories (g50, >450, 80 > 480, >500, >500ms) at baseline and the worst post-baseline value observed
- Frequency counts and percentages of patients having notable ECG values according to the following categories:
  - o QT parameter (QT, QTcF, QTcB, QTcP) increase from baseline > 30 ms, > 60 ms
  - o Newly occurring post-baseline QT parameter > 450 ms, > 480 ms, > 500 ms
  - o HR increase from baseline > 25% and value > 100 bpm
  - o HR decrease from baseline > 25% and value < 50 bpm
  - o PR increase from baseline > 25% and value > 200 ms
  - o Newly occurring post-baseline PR > 200 ms, > 220 ms
  - o QRS increase from baseline > 25% and value > 110 ms
  - o Newly occurring post-baseline QRS > 110 ms, > 120 ms

The denominator to calculate percentages for each category is the number of patients with both a baseline and a post-baseline evaluation. A newly occurring post-baseline ECG notable value is defined as a post-baseline value that meets the criterion post-baseline but did not meet the criterion at baseline.

- Frequency counts and percentages of patients with newly occurring post-baseline qualitative ECG abnormalities (morphology) will be summarized. The denominator to calculate percentages is the number of patients with both a baseline and a post-baseline evaluation. A newly occurring post-baseline qualitative ECG abnormality is defined as a post-baseline abnormal finding which was not present at baseline.

Patients with notable ECG interval values and newly occurring qualitative ECG abnormalities will be listed and the corresponding notable values and abnormality findings will be included in the listings.

Unscheduled ECG measurements will not be used in computing the descriptive statistics for change from baseline at each post-baseline time point. However, they will be used in the analysis of notable ECG changes and the shift table analysis of notable QT parameters.

### Vital signs

Vital sign assessments will be performed in order to characterize basic body function. The parameters collected are weight (kg), body temperature (°C), pulse rate (beats per minute), systolic and diastolic blood pressure (mmHg), and respiration rate (breaths per minute).

Clinically notable elevated values are defined as:

- Systolic BP:  $\geq 160$  mmHg and an increase  $\geq 20$  mmHg from baseline
- Diastolic BP:  $\geq 100$  mmHg and an increase  $\geq 15$  mmHg from baseline.
- Body temperature:  $\geq 39.1^\circ\text{C}$
- Weight: increase from baseline of  $\geq 10\%$
- Pulse rate:  $\geq 120$  bpm with increase from baseline of  $\geq 15$  bpm

Clinically notable below normal values are defined as:

- Systolic BP:  $\leq 90$  mmHg and a decrease  $\geq 20$  mmHg from baseline
- Diastolic BP:  $\leq 50$  mmHg and a decrease  $\geq 15$  mmHg from baseline
- Body temperature:  $\leq 35^\circ\text{C}$
- Weight: decrease from baseline of  $\geq 10\%$
- Pulse rate:  $\leq 50$  bpm with decrease from baseline of  $\geq 15$  bpm

Vital signs shift table based on values classified as notable low, normal, notable high or notable (high and low) at baseline and worst post-baseline will be produced for pulse rate, diastolic BP and systolic BP.

Descriptive statistics will be tabulated for baseline and change from baseline to worst post-baseline value for each vital sign measure.

Patients with clinically notable vital sign abnormalities will be listed. All vital sign assessments will be listed by patient and vital sign parameter.

In the listings, clinically notable values will also be flagged.

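### The vital-sign shift table classifies baseline by criteria that require a change from baseline, so every patient's baseline reads as normal

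*SAP*

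**What the plan says.** The Vital signs part of SAP 2.8.2 defines clinically notable values and then uses them in a shift table. For systolic pressure the high criterion is "Systolic BP: $\geq 160$ mmHg and an increase $\geq 20$ mmHg from baseline". Diastolic pressure follows the same pattern, with a limit of 100 and a rise of 15. For pulse the high criterion is "Pulse rate: $\geq 120$ bpm with increase from baseline of $\geq 15$ bpm". The low criteria mirror these. Systolic pressure needs a value of 90 or less with a fall of 20, diastolic pressure 50 or less with a fall of 15, and pulse 50 or less "bpm with decrease from baseline of" at least 15.

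The section then plans a "Vital signs shift table based on values classified as notable low, normal, notable high or notable (high and low) at baseline and worst post-baseline". The table covers these three parameters, and no separate rule is given for the baseline column.

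Protocol 10.5.3.4 asks for a vital-sign shift table from baseline to the worst on-treatment result. It leaves the definition of notable or abnormal values to the analysis plan and says those values are the ones the shift tables will use. SAP Table 3-1, which records departures from the protocol, does not mention vital signs.

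**The concern.** A shift table is read by comparing each patient's starting category with the worst later one. That works only if the category can be assigned at both times. Here the category includes a change from baseline, which a baseline value cannot have.

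The result is a table whose baseline rows for notable low, notable high and both are empty by construction. An empty row would look like a finding that nobody entered with a low or high value, when in fact the rule does not allow one to be recorded. Patients who entered beyond a limit are merged with those who entered within limits.

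**Working it through.** The documents give no figure to reproduce. The check is one of logic, followed by a small enumeration.

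**Inputs.** From SAP 2.8.2, Vital signs:

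| Parameter | High limit | Rise needed | Low limit | Fall needed |
|---|---|---|---|---|
| Systolic BP (mmHg) | ≥160 | ≥20 | ≤90 | ≥20 |
| Diastolic BP (mmHg) | ≥100 | ≥15 | ≤50 | ≥15 |
| Pulse (bpm) | ≥120 | ≥15 | ≤50 | ≥15 |

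From SAP 2.8.2, Baseline: the baseline is a single value, the last one available up to the start date of study drug.

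**Rule.** Let *b* be the baseline value and *v* the value being classified. Then *v* is notable high if *v* ≥ high limit and *v* − *b* ≥ required rise, and notable low if *v* ≤ low limit and *b* − *v* ≥ required fall.

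**At baseline.** Put *v* = *b*. Both differences are 0, and 0 is below 15 and below 20. All six criteria fail for every possible *b*.

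**Enumeration.** The rule was applied to every whole-number baseline in an assumed range, and then again with the absolute limits alone. The entries count possible values, not patients.

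| Parameter (assumed range) | Values | Notable at baseline, SAP rule | Absolute limits alone: low / normal / high |
|---|---|---|---|
| Systolic BP (50–260) | 211 | 0 | 41 / 69 / 101 |
| Diastolic BP (20–160) | 141 | 0 | 31 / 49 / 61 |
| Pulse (25–220) | 196 | 0 | 26 / 69 / 101 |

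The zeros do not depend on the ranges chosen. The last column shows only that the absolute limits do separate baseline values.

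**Individual patients (illustrative values).**

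| Baseline to worst | Change | SAP table | Absolute limits alone |
|---|---|---|---|
| Pulse 48 to 40 | −8 | normal to normal | low to low |
| Pulse 125 to 130 | +5 | normal to normal | high to high |
| Pulse 125 to 145 | +20 | normal to notable high | high to high |
| Systolic BP 88 to 66 | −22 | normal to notable low | low to low |
| Diastolic BP 48 to 40 | −8 | normal to normal | low to low |

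Two kinds of error appear. A patient who stays beyond a limit is shown as normal throughout. A patient who starts beyond a limit and worsens is shown as having started within it.

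**Comparison within the SAP.** The QT shift tables in the ECGs part of 2.8.2 use absolute millisecond bands, which can be applied at baseline. Criteria there that need a change (heart rate, PR, QRS) are used only for counts of patients, not for a shift table. The vital-sign text joins the two approaches.

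**The case against.** The strongest defence is that the SAP never says the change condition is to be applied at baseline. A sensible programmer would use the absolute limits there, and the text could be called merely silent. That is a fair guess at what might happen, but the SAP defines notable in only one way, names baseline as a time point to be classified with it, and offers no other rule. Protocol 10.5.3.4 ties the shift tables to the plan's own definitions. Followed as written, the output is wrong.

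Other parts of the defence stand and limit the point. A reader might infer any of the following, and the documents do not support them:

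- *That the table cannot show any shift.* It still shows normal to notable low and normal to notable high, which a safety reader mainly wants. What is lost is the baseline dimension.
- *That low pulse at entry is hidden from the report.* The same section tabulates descriptive statistics at baseline for each vital sign, which under SAP 2.1 include the minimum and maximum, and lists all assessments by patient. ECG heart-rate falls of more than 25% to below 50 bpm are counted separately.
- *That the bradycardia count changes.* The SAP defines adverse events of special interest by groupings of preferred terms, not by vital-sign limits.
- *That a pulse falling from 60 to 48, tabulated as normal to normal, shows the flaw.* A baseline of 60 is normal under either rule. That outcome comes from requiring a change of 15 after baseline, which is a defensible choice to avoid flagging small movements.

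Entry criteria narrow the practical effect as well. Exclusion criterion 5 bars systolic BP of 160 or more and diastolic BP of 100 or more, so the high-BP baseline rows would be sparse under any rule, although a Day 1 value could still exceed the limits. The eligibility criteria set no numerical limit on low BP or on pulse, so the loss is mainly there.

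**Conclusion.** The point holds, as a minor one. It is a rule that misclassifies when followed as written, not just a missing detail. For pulse, systolic BP and diastolic BP, every patient with a baseline value is placed in the normal baseline row, whatever the value.

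That statement is a property of the rule. The number of patients misdescribed is the number who entered beyond an absolute limit. The documents give no data on it, and it may be small.

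The conclusion assumes only that the notable criteria are applied at baseline as the SAP states and that baseline is a single value. The consequence stops at this one descriptive safety display in a single-arm study. No endpoint, test or decision rule is touched.

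**What to change.** Add a sentence to the Vital signs part of SAP 2.8.2. For the shift table, baseline and worst post-baseline values are classified by the existing absolute limits alone: systolic BP ≥160 or ≤90 mmHg, diastolic BP ≥100 or ≤50 mmHg, pulse ≥120 or ≤50 bpm. Label the categories low, normal, high, and low and high. Keep the term clinically notable, with the combined absolute-plus-change criteria, for the listings and flags.

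The separate labels matter. Without them, notable would carry two meanings in one section. Because protocol 10.5.3.4 links the plan's notable or abnormal values to the shift tables, the sentence should also say that these limits are the ones meant for that purpose.

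The cost is the sentence and a small programming change. No new threshold or data are needed. The downside is a second set of category labels in the section.
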